Different methodologies have been used to try and increase uptake of contraceptives in the postpartum setting. One study looked at the provision of contraceptives in the home, and found that clients had less days not covered by effective contraceptive use during the 90 days following a first birth [5]. The authors suggested that home dispensing of hormonal contraceptives may improve women's postpartum contraceptive use and should be explored as an intervention in communities where contraceptives are not easily accessible [5]. This study design did not include offering LARC in the home.

A research group from the Department of Obstetrics and Gynecology at the University of Colorado wanted to observe the actual clinical impact that such LARC devices might have on repeat pregnancy and contraceptive continuation rates among adolescents [3]. They conducted a prospective observational study of immediate postpartum implant insertion and found a 2.6% pregnancy rate one year post-placement, compared to an 18.6% pregnancy rate among the control group [3]. Their research shows that high continuation rates of postpartum LARC can translate into reduced immediate postpartum pregnancy rates. Downstream benefits of using LARC in this population also appeared to include a 2-percentage point decrease in preterm birth, which was an unexpected but highly beneficial outcome [3].

This study combines the two prior aforementioned study in a new population; it desires to look at home-based provision of contraceptive care, including LARC in the form of the progesterone-only implant called Jadelle®, and observing how this reduction of a barrier to access increasing uptake of all contraceptives, including abstinence. The hypotheses are:

Hypothesis 1: Offering routinely available contraceptives in a home setting can increase incidence of contraceptive initiation in a postpartum rural Guatemalan population.

Hypothesis 2: Increased use of long-acting reversible contraceptives placed in the home setting in a rural, postpartum Guatemalan population will decrease short-interval pregnancy rates.

Research Objectives: This study has the following objectives:

Objective 1: Increase uptake of routinely offered contraceptives in the postpartum setting by providing them to women at their home-based postpartum visit.

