Based on previously collected data, we expect that during our study timeframe around 260 women will meet eligibility criteria over the course of one year. The clusters will be randomly assigned by a biostatistician. This study, with 200 women enrolled (100 from intervention clusters and 100 from control clusters) will be powered to detect a change in Jadelle uptake rates from 3% to 15% at 85% power and 5% significance, with an intra class correlation of 2%.

[figure not shown]
Group	Proportion Positive	N Per Group	Standard Error	95% Lower	95% Upper
Population 1	0.03	100			
Population 2	0.15	100			
Rate Difference	-0.12	200	0.04	-0.20	-0.04

Alpha= 0.050, Tails= 2, Power = 0.848

Power computation: Normal approximation (unweighted mean p)
Precision computation: Log method

Phase II: Phase two of the study are six month and one-year follow-up visits that occur as part of routine care. Patients are immediately enrolled on delivery into Ninos Sanos, the early childhood health and development program offered through the CHD. Women and infants are seen monthly as part of the program, including routine visits at six and twelve months. At these sessions, mothers will be subject to a questionnaire regarding their contraceptive satisfaction and continuation habits, as well as whether or not they became pregnant since their delivery. This frequent and routine contact will ensure that patients are easily located for performing the follow-up questionnaire, but also will have no problem contacting study personnel if they have issues with their contraception or to report adverse events. We will also hold a focus group (interviews and surveys) for providers regarding their comfort and satisfaction with provision of care in the home setting before the study begins and after enrollment is complete.

Study Flow Diagram:

Study Visits: Patients who participate in the Community Health Services program through the CHD receive routine antepartum counseling on postpartum contraception in their home. At this visit, which is part of routine care, all women receive an educational intervention on contraception, which includes Jadelle® and the risks/side effects, benefits, and alternatives to the immediate postpartum implant.

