continuation, satisfaction, and pregnancy rates. They will have the option to leave the study at any point without any repercussions for their clinical care. We will have these questionnaires performed in a private location, in a one-on-one setting to increase comfort with discussing these issues, and patients will also be able to complete the questionnaire privately if they are literate and do not need assistance.

The primary foreseeable risk of all parts of the study is a breach of privacy and/or confidentiality. Study data will be stored securely in REDCap, which is HIPAA compliant and controls access on a study-by-study basis through the use of unique usernames and passwords. REDCap allows data fields to be flagged as identifiers, and investigators will utilize this feature to remove identifiers from datasets, which are exported for analysis.

Utilization of postpartum contraceptives, including placement of the implant how contraceptive use affects short interval pregnancy rates are the specific aims of this study; the study cannot be performed without offering contraceptives, including device placement. Fortunately, these medications are already in use in the study population and are non-experimental methods. Therefore, with proper counseling and informed consent, we believe the risks of the procedure will be acceptable to the patients and their partners.

Analysis Plan:

Methods & Models: The primary outcome of this study is contraceptive uptake rates in the intervention group. This study, with 200 women enrolled (100 from intervention clusters and 100 from control clusters) will be powered to detect a change in Jadelle uptake rates from 3% to 15% at 85% power and 5% significance, with an intra class correlation of 2%.

The satisfaction surveys will be administered at the six and twelve month well-child visits and will primarily assess patient experience with the medications, including side effects, continuation rates, and pregnancy rates. This quantitative analysis will provide direct feedback in terms of real-world use of contraceptives, their success rates, and their acceptability to the patients, which will also provide baseline research for future interventions to address issues surrounding patient choice of and satisfaction with different method of contraception, including the implant.

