Programs Used: The analysis plan for this will use summary statistics to describe the patient population as well as the outcomes. We will use Student t (normally distributed variables) or non-parametric medians (non-normally distributed variables) tests for continuous data and χ^2 or Fisher's exact tests (for variables with cell sizes <5) for categorical data. Bivariate analyses will be performed to compare the groups. Variables that are significant ($P < 0.05$) in the bivariate analyses will be included in a logistic regression to determine independent predictors of repeat pregnancy. SPSS statistical software (version 24.0.0; IBM SPSS Inc, Chicago, IL) will be used for all the analyses.

References:

2. Guttmacher Institute. Sexual and reproductive health of young women in Guatemala. Online 2014, accessed 1/17/17 (<https://www.guttmacher.org/sites/default/files/factsheet/fb-dd-guatemala.pdf>)
4. LARCs: IUD and Implant Options. Planned Parenthood. Accessed 1/23/17 (<https://www.plannedparenthood.org/planned-parenthood-mar-monte/patient-resources/long-acting-reversible-contraception/larc>)

Timeline: After we have obtained IRAC/COMIRB APPROVAL and Francisco Marroquin University Ethics approval to proceed with the study, we will begin the study. We anticipate the first step of the trial to start January 2018. We expect this to be a 24-month study; the timeline will appear as follows:

Months	Activities
Dec 2017	Training, Jadelle placement refresher course

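### On the cited pregnancy rates, if implant use reaches the repeat-pregnancy model it will usually do so with no pregnancies among users, and ordinary logistic regression then gives no finite odds ratio

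*Combined protocol and SAP*

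**What the plan says.** The Analysis Plan (Programs Used) has two steps for repeat pregnancy. Groups are compared bivariately, with chi-square tests or, where cells fall below 5, Fisher's exact test. Variables reaching P<0.05 are then "included in a logistic regression to determine independent predictors of repeat pregnancy". SPSS 24 is named for every analysis. No exact or penalised method is named, a zero cell is not provided for, and the choice between Wald and likelihood-ratio inference is left open.

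Implant use is not listed as a covariate. It is a natural candidate all the same: Hypothesis 2 says that more long-acting contraception will lower short-interval pregnancy, Objective 3 compares long-acting with short-acting methods, and Procedures to Ensure Ethical Research states that "how contraceptive use affects short interval pregnancy rates are the specific aims of this study".

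Two other statements supply figures. The Background cites a study that "found a 2.6% pregnancy rate one year post-placement, compared to an 18.6% pregnancy rate among the control group". The sample-size text (Phase 1, and again under Methods & Models) plans for "200 women enrolled (100 from intervention clusters and 100 from control clusters"). Its sizing assumption is implant uptake of 3% against 15%, and it names an ICC of 0.02.

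**The concern.** The plan allows for sparse cells in the bivariate tests but not in the model. The implant group will be small and its expected number of pregnancies is below one. A small group enters the model only if its difference is significant, and a group of this size reaches significance mainly when none of its members conceives. That is the configuration in which ordinary maximum likelihood has no finite solution.

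At stake is the adjusted estimate for the exposure behind Hypothesis 2. A report could show a significant bivariate result beside an adjusted odds ratio of practically zero, an interval from zero to infinity and a Wald P near 1. The remedy would then be chosen after the data had been seen. The same applies to any other method category with no pregnancies.

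**Working it through.** **The plan's own figure.** The only computed figure is for uptake, with output "Alpha= 0.050, Tails= 2, Power = 0.848". With p1 = 0.03, p2 = 0.15, mean p = 0.09 and n = 100 per group: z = [0.12·√100 − 1.96·√(2·0.09·0.91)] / √(0.03·0.97 + 0.15·0.85) = (1.200 − 0.793)/0.396 = 1.03, so power = 0.848. It reproduces without any allowance for clustering, which is a separate matter. No figure is given for repeat pregnancy.

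**Inputs**
- Implant users: 15% of 100 plus 3% of 100 = 18, leaving 182 others (sample-size text).
- Upper bound: "around 260 women will meet eligibility criteria" (Phase 1). If all enrolled 1:1, users number 0.15·130 + 0.03·130 = 23.4, about 23.
- One-year pregnancy: 2.6% in users, 18.6% in the others (Background). Assumption: these rates apply here. The Problem section says the pregnancy rate among local implant users is not known, so the others' rate is varied from 15% to 30%.

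**Step 1: an empty implant cell.** Expected pregnancies among users = 18·0.026 = 0.47. P(none) = 0.974^18 = 0.62. It is 0.974^15 = 0.67 with 15 users and 0.974^23 = 0.55 with 23.

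**Step 2: the P<0.05 screen.** Every pair of counts is enumerated with its binomial probability, and the plan's own test is applied to each table.

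| Others' rate (18 v 182) | Passes screen | Zero implant pregnancies, given pass |
|---|---|---|
| 15% | 9% | over 99% |
| 18.6% | 37% | 99.7% |
| 25% | 71% | 87% |
| 30% | 88% | 71% |

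The reason is visible in single tables. With no implant pregnancies, Fisher's P is 0.084 at 32 pregnancies among the 182 others and 0.048 at 33. With one implant pregnancy it is 0.21 at 34 and 0.079 at 45, and falls to 0.047 only at 50. The expected number at 18.6% is 182·0.186 = 34.

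The chance that the term both enters and is separated is the product of the two columns: 0.371·0.997 = 0.37 at 18.6%; 0.71·0.87 = 0.62 at 25%; 0.88·0.71 = 0.62 at 30%. It cannot exceed the 0.62 of Step 1.

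**Step 3: what the model returns for the expected table, 0/18 v 34/182**

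| Method | Result |
|---|---|
| Fisher's exact (the screen) | P = 0.047 |
| Ordinary ML, 20 iterations | log OR −19.7, SE about 9,474, Wald P = 0.998 |
| Ordinary ML, 25 iterations | log OR −24.7, SE about 115,400, Wald P = 0.9998 |
| Likelihood-ratio test | chi-square 7.06 on 1 df, P = 0.008 |
| Firth, profile penalised likelihood | OR 0.12, 95% CI 0.0009 to 0.89, P = 0.035 |

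The ML coefficient grows with each iteration, so the printed odds ratio and standard error depend on where the software stops. The separation is quasi-complete: users show one outcome only, non-users show both. All these figures treat women as independent.

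**The case against.** A reader might infer that the model will usually fail, or that it will report the implant as non-significant. The documents support neither.

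- **The screen comes first.** On the cited rates implant use is left out of the model in about 63% of trials, and the model then says nothing about it. With 15 users against 185 others it enters in only about 15%. Separation in the fitted model is a minority outcome in the base case. This stands, and the point is therefore conditional on entry.
- **The near-1 P is the Wald test only.** The likelihood-ratio P on the same fit is 0.008, and the plan does not say which it would use. Any variable in the model has also just been significant bivariately, so the association would not vanish from the report. This stands. It does not supply a finite odds ratio or a usable Wald interval.
- **The contrast is inferred.** The plan does not specify implant users against everyone else. Objective 3 concerns long-acting against short-acting methods provided in the home, and the Background counts IUDs as long-acting. Within the intervention arm alone (15 v 85) the screen is passed in about 10% of trials. This limits how often the problem would arise.
- **The rates are borrowed.** If the other women conceive more often, the zero-cell share falls: with 23 users of 260 it is 97% at 18.6%, 67% at 25% and 57% at 30%. It is still the more common case across that range.
- **The analysis is secondary.** The primary outcome is uptake, and a zero cell is plain in the output. That argues for moderate weight, but a method picked after the empty cell is seen is no longer prespecified.

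**Conclusion.** The point holds in conditional form. Given 18 users of 200, rates of 2.6% and 18.6%, and implant use as a candidate variable, the term enters the model in about 37% of trials, and in 99.7% of those the implant cell is empty. Over assumed rates of 15% to 30% in the other women, entry ranges from 9% to 88%; at 25% and 30% the zero-cell share is 87% and 71%. In each such case the planned estimator gives no finite odds ratio and no usable Wald interval, in the data where protection looks clearest.

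The size rests on rates from another population, on a contrast the plan does not spell out, and on independence between women. It is a weakness of a secondary analysis that serves a stated hypothesis. It should be corrected, but it does not touch the primary comparison.

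**What to change.** Under Programs Used, state that the repeat-pregnancy model will be fitted by Firth penalised-likelihood logistic regression, with P values and 95% confidence intervals from the profile penalised likelihood and not from Wald statistics. Allow software other than SPSS 24 for this one model if the installed version does not offer it.

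The cost is one sentence and perhaps a second package, with no extra data and no burden on participants. The downside is slight shrinkage of odds ratios toward 1 where events are plentiful.

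The change leaves two problems in place. The P<0.05 screen would still exclude implant use in about 63% of base-case trials; prespecifying it as a covariate would deal with that. The six clusters are also still ignored, so the Firth interval and P = 0.035 above may be too optimistic. Both need their own amendments.
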